central status, subject specific random intercept will be introduced to model correlation due to repeated measurements. A generalized linear mixed model will be used with the two response variables (self-report pain questionnaires and experimental pain testing scores). The form of the link function and variable transformations will be determined based on the data using AIC criteria. A full likelihood model-based approach will be used to fit the model. Hypotheses will be tested by the likelihood ratio test. A clinically relevant response is defined as 50% reduction in pain within the patient. The following effects are hypothesized based on our pilot studies: Central patients will constitute approximately 30% of the breast cancer population; 10% of non-central patients are hypothesized to show clinically relevant improvement under DLX while the rate of at least 70% is hypothesized in the central group. Overall, this leads to the expected 28% response rate. Placebo effects in this kind of studies are expected not to exceed 3%. Conservatively we would be looking to detect improvement over twice the expected placebo rate (6%). Using a two-sided test for the proportion of improvement vs. 6% at $\alpha=0.05$ we will have the power of 81% with 21 patients in each "bin" (total of 84 patients).

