13.0 Data and Safety Monitoring

This is a phase II trial that does not require an independent data and safety monitoring board because it is designed to look at mechanism of effect rather than efficacy. Monitoring of accrual and adverse events will be performed by UM investigators and research personnel during (1) routine weekly Breast Oncology Program research meetings which are attended by faculty and staff, research nurses, and data management and regulatory personnel from the University of Michigan Clinical Trials Office and (2)

quarterly Chronic Pain and Fatigue Research Center meetings which are attended by the co-Investigators and study coordinator listed on the protocol. In addition, the trial will be monitored quarterly by the UM Comprehensive Cancer Center DSMB per institutional guidelines.

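### The sample size rests on testing an open-label response rate against an unsourced fixed 6%, so rejecting 6% would not show that duloxetine beats placebo

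*Combined protocol and SAP*

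**What the plan says.** Amendment 7 and Section 4.0 convert the placebo-controlled crossover into a single-arm, open-label study. Section 4.0 argues that this is harmless for the predictor question because placebo response should fall equally on patients with and without centralized pain.

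Section 11.0 (Analysis, Aim 2) then sets up the sample size:

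- Response: "A clinically relevant response is defined as 50% reduction in pain within the patient".
- Central share: "Central patients will constitute approximately 30% of the breast cancer population".
- Non-central response: "10% of non-central patients are hypothesized to show clinically relevant improvement under DLX".
- Central response: "the rate of at least 70% is hypothesized in the central group".
- Combined: "Overall, this leads to the expected 28% response rate".
- Placebo: "Placebo effects in this kind of studies are expected not to exceed 3" per cent.
- Benchmark: "Conservatively we would be looking to detect improvement over twice the expected placebo rate (6", that is, 6%.

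The test is two-sided at 0.05 against 6%, with 81% power claimed for 21 patients in each of four treatment bins (84 in total). No other analysis in Section 11 has a power statement. Centrality is studied in a separate generalized linear mixed model with a drug-by-centrality random effect and likelihood ratio tests.

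**The concern.** With no placebo arm, the 6% is the only stand-in for a comparator. It is twice an upper limit of 3% for which Section 11 gives no study, data or interval. The pilot of duloxetine described in Section 2.0 was itself open label, so it supplies no placebo rate. Calling 6% conservative is therefore unsupported.

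Section 4.0's argument does not carry over to this test. If placebo response is equal in central and non-central patients, it cancels when the two groups are contrasted. In a one-sample test against a constant nothing cancels, and every non-drug source of improvement adds to the observed rate. The protocol contains several such sources:

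- Treatment is open label.
- Cases must report worst pain of 5 or more (Section 5.4), and Amendment 6 describes this pain as intermittent, so regression to the mean is likely.
- Physical therapy, chiropractic and massage are allowed during the study (Section 7.1).

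At stake is the reading of the only result with stated power. A rejection of 6% could be taken as duloxetine outperforming placebo, which this design cannot establish.

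**Working it through.** **1. Reproduce the plan's figures.** Inputs are from Section 11.

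Expected rate: 0.30 × 0.70 + 0.70 × 0.10 = 0.21 + 0.07 = 0.28, as stated.

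Power by the arcsine method, Φ(h√n − 1.96), with h = 2·asin√0.28 − 2·asin√0.06 = 1.1152 − 0.4949 = 0.6203:

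- n = 21: 0.6203 × 4.583 = 2.842; Φ(0.882) = 81.1%. This matches the stated 81%, which is therefore the power within one bin.
- n = 84: above 99%.

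Exact power per bin at 28% is 74% or 88%, according to which exact rule below is used.

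**2. Rejection rules for 6%.** The plan does not name the test, so two exact two-sided versions bracket the answer. Only upward rejection is counted.

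- Equal-tail: 5 or more of 21; 11 or more of 84.
- Probability-ordered: 4 or more of 21; 10 or more of 84.

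**3. Chance of rejecting 6% when the drug adds nothing.** This is P(X ≥ r) for X ~ Binomial(n, background rate). The 3% and 6% are the plan's figures. The 10%, 15% and 20% are assumed background rates, shown as a range because the documents give no observed placebo rate.

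| Background rate | One bin, n = 21 (r = 5 / r = 4) | Pooled, n = 84 (r = 11 / r = 10) |
|---|---|---|
| 3% | 0.03% / 0.3% | 0.004% / 0.02% |
| 6% | 0.7% / 3.4% | 1.2% / 2.9% |
| 10% | 5.2% / 15.2% | 21.6% / 33.0% |
| 15% | 19.7% / 38.9% | 73.2% / 82.8% |
| 20% | 41.4% / 63.0% | 96.3% / 98.2% |

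Pooling raises power, but it also makes the test more sensitive to a benchmark set too low.

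**4. Power if the benchmark moves, with 28% still expected.** Arcsine throughout, so that it compares with the plan's 81%.

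- Against 10%: h = 1.1152 − 0.6435 = 0.4717. For n = 21, h√n = 2.162 and power is Φ(0.202) = 58% (exact 56%, 6 or more of 21). For n = 84, h√n = 4.323 and power is Φ(2.363) = 99% (exact 99%, 15 or more of 84).
- Against 15%: h = 0.3198. For n = 84, h√n = 2.931 and power is Φ(0.971) = 83%.
- Against 20%: h = 0.1879. For n = 84, h√n = 1.722 and power is Φ(−0.238) = 41%.

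**The case against.** The strongest reply is that the plan is coherent on its own figures. With placebo response at or below 3%, a threshold of 6% leaves a margin, and false rejection is negligible. That stands: the difficulty depends on the true background rate being higher than the plan assumes, and the documents do not show that it is.

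A reader might infer that the 10% for non-central patients contradicts the 6%, because a group not expected to benefit already exceeds the no-effect benchmark. The documents do not support this. The 10% is a response rate on duloxetine, not a no-drug rate. If placebo response were 3%, rejecting 6% when the true rate is 10% would be a correct finding about the drug. For the same reason 10% has no special standing as a replacement null. The 10% shows only that rejecting 6% would not demonstrate a centrally mediated effect.

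Nor does the plan infer centrality from the 6% test, because the mixed model addresses it. What remains is that this model, which serves Objective 2, has no stated power.

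A reader might also infer that the plan promises a declaration of superiority over placebo. It does not. The wording belongs to the sample-size justification, no success rule is attached, and the 50% response is not among the listed primary or secondary outcomes. Section 13's statement that "it is designed to look at mechanism of effect rather than efficacy" explains why no independent monitoring board is required; it does not rule out a response-rate calculation.

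Finally, the size depends on the exact test chosen, and no rule based on any one of the four bins is in the plan. Both exact tests are therefore shown, and no any-bin figure is relied on.

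**Conclusion.** The point holds as a limit on interpretation. The 81% is computed correctly for one bin of 21. However, the test it describes compares an open-label rate with an assumed constant, and it cannot separate drug effect from other improvement on study. Its false-rejection risk runs from negligible at a 3% background rate to 22-33% pooled at 10% and 96-98% pooled at 20%. Per bin, the corresponding figures are at most 0.3%, then 5-15% and 41-63%. Background rates above 6% are assumptions, and nothing in the documents establishes which rate applies. That uncertainty is the weakness: the inference rests on a figure that is unsourced and that the single-arm design cannot test.

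**What to change.** In Section 11:

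- Report the 50% response rate, pooled (n = 84) and by bin (n = 21 each), with exact 95% confidence intervals, described as improvement during open-label duloxetine.
- State that rejecting 6% is not evidence of superiority to placebo. Give the source of the 3%, or label it as an assumption.
- If a test is kept, make it pooled, call it a comparison with an assumed benchmark, and show results over a range of benchmarks, for example 6% to 20%.
- Restate power with one named method across that range. By arcsine with n = 84 it is above 99% against 6%, 99% against 10%, 83% against 15% and 41% against 20%. If per-bin power is reported against 10%, it is 58% by arcsine or 56% exact.

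This is a change of wording and analysis only, with no extra patients or visits. The cost is the loss of the placebo-referenced inference and a per-bin power figure less favourable than 81%.

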12.0 Data Handling

MICHRs Data Management (DM) unit supports research at the University of Michigan by providing expertise in all areas of data management, from study start to completion, meeting best practices and ensuring data integrity. DM works closely with each study team to help develop an efficient method of data collection and management based on project needs, following Standard Operating Procedures and Good Clinical Practice. The unit creates study-specific data collection instruments either as paper or electronic Case Report Forms (CRFs). Database development is done using web-based applications. Throughout the life of the project, this unit provides the necessary services and expertise to help manage and report data. DM will track and store Case Report Forms, perform data entry and provide a number of reports to monitor data quality and study progress. The Data Management Unit also works collaboratively with other MICHR units to provide researchers with comprehensive services needed to effectively conduct research. The self-report data will be collected via REDCap, an electronic data capturing system developed at Vanderbilt University. REDCap is an open-source, secure, web-based application designed to support data capture for research studies, and is provided through MICHR. REDCap provides: 1) an intuitive interface for data entry; 2) audit trails for tracking data manipulation and export procedures; 3) automated export procedures for seamless data downloads to common statistical packages; 4) procedures for importing data from external sources; and 5) advanced features, such as branching logic and calculated fields within electronic forms. Servers are physically located in the UM Medical School Information Systems data center. Physical security for the databases is provided in a professionally managed and equipped tier-2 data center with tightly controlled access. Remote data access employs SSL encryption and 2-tier Kerberos and UMHS level 2 password challenges via LDAP authentication. Access to the application, the database, and the underlying systems infrastructure comply with industry best practices, supporting HIPAA security and privacy requirements and the HITECH Act. Backup of data is managed by MSIS, and vulnerability testing is performed regularly. Daily backups and VM snapshots of the application and database servers are stored on a remote storage device.

13.0 Data and Safety Monitoring

This is a phase II trial that does not require an independent data and safety monitoring board because it is designed to look at mechanism of effect rather than efficacy. Monitoring of accrual and adverse events will be performed by UM investigators and research personnel during (1) routine weekly Breast Oncology Program research meetings which are attended by faculty and staff, research nurses, and data management and regulatory personnel from the University of Michigan Clinical Trials Office and (2)

quarterly Chronic Pain and Fatigue Research Center meetings which are attended by the co-Investigators and study coordinator listed on the protocol. In addition, the trial will be monitored quarterly by the UM Comprehensive Cancer Center DSMB per institutional guidelines.

15.0 APPENDICES

The following documents have been attached as appendices to this protocol:

1. Brief Pain Inventory (BPI)
2. Michigan Body Map
3. Symptom Severity Scale
4. PainDETECT
5. FACT/GOG-NTX
6. PROMIS (Physical function-SF)
7. PROMIS (Fatigue-SF)
8. PROMIS (Sleep disturbance-SF)
9. Hospital Anxiety and Depression Scale (HADS)
10. Multiple Ability Self-Report Questionnaire (MASQ)
11. Demographics
12. Cymbalta (duloxetine) Highlights of Prescribing Information
13. Concomitant medication form
14. Medication log

Concomitant Medications

Subject ID: _____ Date: _____

Please list any prescription and nonprescription drugs, vitamins and dietary supplements that you have taken since your last clinic visit.

Drug name	Total Daily Dosage	Why do you take the medication?	Is this a medication you take daily?	Start Date (if not a daily medicine)	End Date (if not a daily medication)

Reviewed by: _____

Medication Log

Subject ID: _____

Please record when you take your study medication on this log. You should take your medication in the morning at approximately the same time each day, including the days that you have your study visits.

Please list any problems that you had (e.g., forgot to take medication, too much nausea, etc) in the comments box. If you are having side effects that are causing you to not take the medication, please call [name] at [contact].

Date	Bottle Number	Time	Comments	Date	Bottle Number	Time	Comments
	1				2		
	1				2		
	1				2		
	1				2		
	1				2		
	1				2		
	1				2		
	2				2		
	2				2		
	2				2		
	2				2		
	2				2		
	2				2		
	2				2		
	2				2		
	2				2		
	2				2		
	2				2		
	2				2		
	2				2		
	2				2		

Reviewed by: _____
